## LIST OF ABBREVIATIONS

AE	Adverse Event
AS	Aortic Stenosis
CAD	Coronary Artery Disease
CFR	Coronary Flow Reserve
CRF	Case Report Form
CV	Cardiovascular
FFR	Fractional Flow Reserve
GLS	Global Longitudinal Strain
IC	Informed consent
iFR	Instantaneous wave-free ratio
IMR	Index of Microcirculatory Resistance
IRB	Institutional Review Board
LVEDP	Left Ventricular End Diastolic Pressure
LV	Left Ventricular
MACE	Major Adverse Cardiovascular Events
MI	Myocardial Infarction
MVD	Microvascular Disease
NA	Not Applicable
NHPR	Non-Hyperemic Pressure Ratio
NSTEMI	Non-ST-elevation Myocardial Infarction
RFR	Resting full-cycle ratio
SAE	Serious Adverse Event
SAP	Statistical and Analytical Plan
SPECT	Single-photon emission computed tomography
STEMI	ST-elevation Myocardial Infarction
SAVR	Surgical aortic valve replacement

TAVI/R

Transcatheter aortic valve implantation/ Replacement

## PROTOCOL SUMMARY

Aortic stenosis (AS) is the most common primary valve disease leading to surgery or catheter intervention in Europe, with a growing prevalence due to the aging population. Severe AS is associated with significant morbidity and mortality and is treated by surgical valve replacement (SAVR) or transcatheter aortic valve implantation (TAVI). However, significant coronary artery disease (CAD) is reported in more than 60% of patients with AS, and this concomitant CAD needs to be correctly assessed because untreated significant CAD is associated with adverse outcomes. Current guidelines recommend intra-coronary pressure measurement using either fractional flow reserve (FFR) or non-hyperemic pressure ratios (NHPR) for the assessment of intermediate coronary artery lesions before revascularization. However, correctly identifying hemodynamically significant coronary stenoses by FFR or NHPR is difficult in patients with AS because of the hypertrophic remodeling related to the valve pathology, which interferes with coronary blood flow in the microcirculation and reduces the accuracy of FFR and NHPR. This has resulted in substantial controversy in this field of coronary artery disease and there is currently no clear guideline for the management of AS patients with concomitant CAD. Recent technological advances now permit the concomitant evaluation of FFR/NHPR and microcirculatory function at the time of cardiac catheterization. Using this technology, we will simultaneously evaluate the hemodynamic significance of coronary stenoses (using FFR and a NHPR - Resting Full cycle Ratio [RFR]) and the microcirculatory function (Index of Microcirculatory Resistance, IMR) in patients with AS and CAD prior to SAVR/TAVI. One hundred patients with AS and intermediate CAD will be included in the study. Of them Eighty will undergo AVR and at least 58 will undergo the follow-up at 6 Months. During routine pre-valve replacement cardiac catheterization, measurement of intermediate CAD lesions (by FFR and RFR) and IMR will be performed in duplicate using new software. These measures of CAD severity will be compared with a gold standard non-invasive test (single photon emission computed tomography [SPECT]). This will validate the use of RFR and determine if IMR can be used to improve the ischemia prediction of FFR. In addition, the patients undergoing TAVI the LVEDP will be measured immediately before and after valve implantation and FFR, RFR and IMR will be measured after valve implantation. Subsequently, when these patients undergo a post-intervention (whether SAVR or TAVI) evaluation 6 months after valve replacement, the effect of valve replacement on FFR, RFR and IMR (again in duplicate) will be determined. This will be the first study measuring these parameters before and 6 months after valve replacement. The data will be used to calculate a 'corrected' FFR (or RFR) based on microcirculatory function in these patients, which can then be used in the future to correctly evaluate CAD pre-intervention in patients with AS. This will translate into more efficient management of patients with AS. Fewer of these patients will unnecessarily undergo coronary artery bypass grafting or stenting when the CAD does not need to be treated and, conversely, in those who do require treatment of the CAD, revascularization can be carried out during a single surgery/intervention, avoiding multiple high risk procedures in patients who are already at high peri-operative/peri-interventional risk.

[figure not shown]

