## 1. BACKGROUND

Aortic stenosis (AS) is the most common primary valve disease leading to surgery or catheter intervention in Europe, with a growing prevalence due to the aging population. Severe aortic valve stenosis, defined by a mean gradient over the aortic valve of greater than 40mmHg or an aortic valve area of less than 1.0cm^2, is associated with significant morbidity and mortality and is treated by surgical valve replacement (SAVR) or transcatheter aortic valve implantation (TAVI). However, significant coronary artery disease (CAD) is reported in more than 60% of patients with AS, and needs to be correctly assessed because untreated significant CAD is associated with adverse outcomes.

Current guidelines recommend intra-coronary pressure measurement using either fractional flow reserve (FFR) or non-hyperemic pressure ratios (NHPRs) for the assessment of intermediate coronary artery lesions before revascularization. A FFR of  $\leq 0.80$  or a NHPR of  $\leq 0.89$  is considered to indicate that a coronary lesion is significant. Non-hyperemic pressure ratios include the instantaneous wave-free ratio (iFR) and the resting full cycle ratio (RFR), which have been shown to be comparable. However, correctly identifying hemodynamically significant coronary stenoses is difficult in patients with AS because of the hypertrophic remodelling related to the valve pathology. Aortic stenosis is associated with a significant increase in left ventricular (LV) mass resulting in pathological changes in coronary and LV hemodynamics, which are associated with coronary microvascular dysfunction.

With the development of microvascular dysfunction, intra-coronary pressure measurements become less reliable and, currently, whether FFR, or the NHPRs, can reliably detect myocardial ischemia in patients with severe AS is controversial, making it difficult for physicians to correctly determine whether or not coronary lesions should be revascularized prior to TAVI or at the time of SAVR. Yamanaka *et al.* recently reported a strong correlation of iFR with FFR in patients with

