### Secondary outcomes

2. Measurement of IMR in patients with AS prior to intervention and 6 months after SAVR/TAVI.
  - a. Description of the range of IMR values in a cohort of patients with severe AS.
    - i. Do all patients with severe AS have high microvascular resistance as assessed by IMR?
    - ii. Does IMR change significantly 6 months after TAVI/SAVR? If there is a significant decrease in IMR then this indicates that microcirculatory function improves 6 months after aortic valve intervention.
3. Null hypothesis: the “corrected” FFR (at baseline; based on baseline IMR) does not correlate with the post-intervention FFR.
  - a. If the null hypothesis is upheld then a correction of FFR using baseline IMR does not improve the validity of FFR in patients with severe AS.
4. Null hypothesis: using IMR at baseline does not improve the ischemia prediction of FFR. Ischemia is measured by SPECT (Figure 2).
  - a. If the null hypothesis is upheld then IMR does not improve stratification of coronary ischemia based on FFR.

- b. If a significant proportion of patients with SPECT ischemia have a raised IMR this would support the hypothesis that IMR can be used to correct falsely high (negative) FFR measurements.
- 5. Comparison of the diagnostic performance of FFR and RFR with SPECT ischemia (and compare with findings of Yamanaka *et al*).
- 6. Reproducibility of the FFR, RFR and IMR

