## Secondary outcomes

- 1. A description of the range of IMR values in a cohort of patients with severe AS will be a novel and important contribution to the field of interventional cardiology. Furthermore, the change in IMR (microvascular function) in response to valve replacement will be an important finding in this study. If there is a significant decrease in IMR then this indicates that microcirculatory function improves 6 months after aortic valve intervention. Since microvascular function predicts outcomes in patients with AS, IMR evaluation at 6 months after TAVI/SAVR might provide an additional method to risk stratify these patients even after correction of the valve pathology.
- 2. If the “corrected” FFR (at baseline; based on baseline IMR) does not correlate with the post-intervention FFR then a correction of FFR using baseline IMR does not improve the accuracy of FFR in patients with severe AS.
- 3. Compared with SPECT, a correlation of FFR and RFR will be an important contribution. Firstly, this will be a validation of RFR as a resting measure of ischemia in AS patients. Secondly, these data will support the data of a previous study with a different resting measure of ischemia (iFR) or the findings may be in conflict with the previous study, which would be important.

4. Using SPECT as a standard of myocardial ischemia, IMR may improve the ischemia prediction of FFR. This would be an extremely important finding, supporting the routine use of IMR in patients with microvascular disease when coronary artery lesions need assessment by FFR. Because AS is an important clinical condition with reversible microvascular dysfunction, this provides an excellent naturally occurring model for the study of microvascular function and CAD. These findings will be useful in other groups of patients who also have microvascular dysfunction (including patients with heart failure, obesity, diabetes, liver disease, chronic kidney disease and heart transplant patients). Being able to factor-in microvascular dysfunction (using simultaneously measured microvascular resistance) at the time of FFR measurement will permit accurate assessment of the severity of CAD in these patients. This study has the potential to revolutionize the assessment of coronary artery lesions, not just in patients with AS, but in all patients with CAD since the validity of CAD assessment by FFR/NHPRs may, indeed, depend on microvascular function.

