### 3.6 Exclusion criteria

1. The procedure is an emergency and/or the patient is unstable.
2. Pregnancy or lactation
3. Haemodynamically unstable patients

4. Killip class III-IV
5. Previous CABG
6. Contra-indications for adenosine administration: severe asthma or pre-existing type 2 AV-block
7. No significant coronary artery disease (<50% stenosis on angiography).
8. Critical coronary artery disease deemed by the Heart Team to require revascularization.
9. Patients will be excluded from the SPECT study (secondary objective) if they have a left main coronary stenosis >50%, severe triple vessel disease, previous myocardial infarction in the same coronary artery & tandem lesions (separated by >10mm) requiring independent evaluation in the same coronary artery since these factors interfere with the SPECT analysis.

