At this time three boluses of room-temperature saline are administered in order to measure the intra-coronary flow during hyperemia by the method of thermodilution. This extra step, which is investigational, adds no additional risk or cost to the patient. However, it permits the calculation of flow and microvascular resistance or IMR (index of microvascular resistance) using Coroflow® software (Coroventis, Uppsala, Sweden). IMR is already clinically indicated in several other groups of patients (with suspected microvascular dysfunction) and is used on a routine basis in patients in our cardiac catheterization laboratory.

In order to assist the Heart Team in deliberation over the ischemic importance of intermediate coronary lesions, SPECT imaging is clinically indicated during the pre-operative/interventional work up. This will be carried out in the Department of Nuclear Medicine according to routine clinical practice under the guidance of [name]. If adenosine cannot be used then regadenoson will be used.

Intra-coronary assessment of intermediate lesions is part of routine clinical practice. The decision to revascularize and the method of revascularization (percutaneous coronary intervention versus coronary artery bypass grafting) of patients with aortic stenosis based on intra-coronary measurements and non-invasive measures of ischemia (SPECT) is discussed by the Heart Team (including the cardiologist and cardiothoracic surgeon) and forms part of routine clinical practice. In patients who do not undergo immediate revascularization, the residual CAD should be reassessed after SAVR/TAVI. Current controversy about the validity of both intra-coronary and non-invasive tests in patients with AS necessitates further evaluation (after valve intervention) since coronary lesions should not be unnecessarily treated (Class III recommendation in the ESC guidelines).

In the patients who will undergo TAVI measurements of LVEDP will be carried out during the TAVI procedure immediately before and after valve implantation. As the catheters are already present in the ventricle of the patient at this point this does not require an extra intervention

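### Objective 4 would credit IMR with correcting falsely high FFR from baseline SPECT alone, which cannot rule out that SPECT is itself positive through microvascular disease

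*Combined protocol and SAP*

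**What the plan says.** The Protocol Summary introduces SPECT with the words "These measures of CAD severity will be compared with a gold standard non-invasive test". In the study objectives, secondary outcome 4 makes SPECT the measure of ischaemia and tests whether baseline IMR improves on FFR. Item 4b adds: "If a significant proportion of patients with SPECT ischemia have a raised IMR this would support the hypothesis that IMR can be used", the use in question being to correct FFR readings that are falsely high. Item 4 of the expected secondary outcomes builds on this: "Using SPECT as a standard of myocardial ischemia, IMR may improve the ischemia prediction of FFR". It says such a finding would support routine use of IMR when lesions are assessed by FFR in patients with microvascular disease.

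Other parts of the protocol bear on how SPECT can be read. The Background says AS brings "pathological changes in coronary and LV hemodynamics, which are associated with coronary microvascular dysfunction". Section 3.8 says: "Current controversy about the validity of both intra-coronary and non-invasive tests in patients with AS necessitates further evaluation", and places that further evaluation after the valve intervention. Section 3.6, item 9 removes certain patients from the SPECT study "since these factors interfere with the SPECT analysis"; microvascular disease is not among the factors listed. The schedule of events marks SPECT at baseline, and at 6 months only in brackets.

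Secondary outcome 3 tests whether the IMR-corrected baseline FFR correlates with post-intervention FFR. Section 9.2 plans an ROC analysis of RFR against SPECT. It gives no analysis for IMR added to FFR.

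**The concern.** A positive baseline SPECT with a normal FFR has two possible explanations. Either the FFR is falsely high and the lesion matters, or the FFR is right and SPECT is positive because of the microcirculation. IMR would be associated with SPECT in both cases. Item 4b considers only the first.

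Item 4b also looks only at SPECT-positive patients. Without the SPECT-negative group, the reader cannot tell whether raised IMR goes with ischaemia at all or is simply common in this cohort.

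At stake is the claim that IMR corrects FFR, which the protocol expects to extend to other patients with microvascular dysfunction. Objective 4 as written could be declared positive without reference to objective 3, the one place where the IMR correction meets a measurement made after the valve has been treated.

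**Working it through.** **1. The plan's own figures.** Objective 4 has no sample size of its own. The 80 in section 9.1 is for the FFR versus RFR comparison. With the Hanley–McNeil variance V, AUC 0.70 against 0.50, two-sided alpha 0.05 and 90% power (the plan prints 0.90%, read here as 90%), the condition is 1.96√V₀ + 1.282√V₁ ≤ 0.20. The SPECT-positive prevalence is not given. Assuming 30%, 40% or 50%, the required N is 102, 87 or 82 with the null variance for V₀, and 95, 80 or 72 with the alternative variance throughout. So 80 is reachable at about 40–50%, and I take it as given. For the 6-month data, a paired t-test with difference 0.03, SD of the difference 0.08 and power 0.80 reproduces 58. After 25% drop-out, 80 × 0.75 = 60 remain.

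**2. The item 4b rule alone.** If IMR and SPECT are unrelated, the proportion with raised IMR among SPECT-positive patients equals that in the whole cohort. Objective 2 asks whether all patients with severe AS have high IMR. If they do, the proportion is 100% in both SPECT groups and item 4b is met without carrying any information.

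**3. FFR undistorted, SPECT partly microvascular (illustration).**
- From section 9.1: FFR mean 0.82, SD 0.08.
- Assumed: measurement SD 0.02; IMR independent of FFR; SPECT positive if true FFR ≤0.80 or IMR is in the top fraction q; then 15% of results flipped at random.
- AUC from 200,000 simulated patients. Likelihood-ratio test of IMR added to FFR in logistic regression, 400 samples of 80.

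| q | AUC, FFR | AUC, FFR + IMR | IMR significant |
|---|---|---|---|
| 0 | 0.832 | 0.832 | 7% |
| 10% | 0.793 | 0.805 | 35% |
| 20% | 0.759 | 0.793 | 64% |
| 30% | 0.728 | 0.787 | 84% |

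Repeat runs gave 3–7%, 33–37%, 64–68% and 83–84%. The first row is the nominal 5% within simulation error.

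**4. Can SPECT tell the two explanations apart?** A second model, all parameters assumed: epicardial severity E and microvascular disease M are independent standard normals. Lesion severity as read by FFR = E − cM + noise (SD 0.5). IMR = M + noise (SD 0.5). SPECT = E + bM + noise (SD 0.8), with the top 30% positive. n = 80.

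| Situation | AUC against SPECT, FFR → FFR + IMR | IMR significant | AUC against true epicardial severity |
|---|---|---|---|
| Neither affected (c = 0, b = 0) | 0.836 → 0.836 | 3% | 0.94 → 0.94 |
| SPECT affected (c = 0, b = 0.3) | 0.827 → 0.843 | 43% | 0.94 → 0.94 |
| SPECT affected (c = 0, b = 0.6) | 0.803 → 0.857 | 89% | 0.94 → 0.94 |
| FFR falsely high (c = 0.6, b = 0) | 0.793 → 0.826 | 67% | 0.88 → 0.93 |

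Against SPECT, the last two rows look alike. Against a reference free of the microvascular effect they part: IMR adds nothing in one and helps in the other. The nearest such reference in the study is the 6-month FFR of the same lesion, because the Background anticipates normal microvascular function by then. A SPECT-negative comparison repairs step 2, but it does not by itself separate these two rows.

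**5. How to use the 6-month FFR.** Assume baseline FFR really is inflated by 0.02–0.04 per SD of IMR and the SD of change is 0.07–0.08. The chance that IMR is significant when added to baseline FFR is then:

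| n | 6-month FFR ≤0.80 (yes/no) | 6-month FFR, continuous |
|---|---|---|
| 58 | 15–50% | 36–89% |
| 80 | 22–59% | 43–94% |

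A second illustration at n = 58 gave 21–59% against 32–90%. The levels move with the assumed error in IMR; the ordering does not.

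**The case against.** The strongest reply is that objective 3 already compares IMR-corrected FFR with post-intervention FFR, and that the Background derives the correction from the 6-month measurements. This stands, and it rules out a stronger reading. A reader might infer that the correction would be learned from baseline SPECT and so push patients with microvascular disease towards unnecessary revascularisation. The plan describes no such procedure. What remains is that the conclusions of objectives 3 and 4 are not linked.

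Second, the documents nowhere say that SPECT turns positive through microvascular disease. That stands too: the mechanism is an assumption, and the simulated percentages do not estimate this study's error rate. Figure 2, which illustrates this objective, is not available in the text, and its legend lists microvascular dysfunction beside SPECT, so it may say more.

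Third, a reader might extend the point to objective 5, "Comparison of the diagnostic performance of FFR and RFR with SPECT ischemia". The IMR argument does not reach it. SPECT is kept there so that results can be set beside an earlier study using the same standard, which is a sound reason. Using 6-month FFR instead would also favour baseline FFR over RFR.

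Finally, the 6-month data are selective. Section 3.8 has revascularisation decided partly on SPECT and intra-coronary results, and section 9.1 takes revascularised patients out of follow-up. This limits 6-month FFR as a reference. It does not rescue the inference from SPECT alone.

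**Conclusion.** The point holds for objective 4. Item 4b and the matching expected outcome would read an association between IMR and baseline SPECT as proof that FFR was falsely high, under conditions in which the protocol itself doubts non-invasive tests. The design can show the association, but baseline SPECT cannot show which explanation is right.

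The size is unknown. If SPECT is unaffected by microvascular disease, the false-positive rate stays at its nominal level. If 10–30% of patients are SPECT-positive for that reason, IMR would be significant in roughly a third to more than four fifths of studies of 80 patients with no FFR distorted. The value of 6-month FFR as a check rests on the protocol's expectation that microvascular function recovers by then.

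The primary endpoint is not affected, and the documents do not support a claim of patient harm or of a flaw in objective 5. The change is worth making because it stops an unsound inference at little cost.

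**What to change.** 1. Replace the item 4b rule. Among patients with FFR above 0.80, compare IMR between SPECT-positive and SPECT-negative patients. Add to section 9.2 a test of IMR added to FFR against SPECT.
2. State in the objectives that a positive result against baseline SPECT alone shows an association with perfusion ischaemia. The claim that IMR corrects falsely high FFR should also need support from the 6-month FFR of the same lesion. Analyse that as a continuous outcome, with baseline FFR with and without IMR, an estimate and a confidence interval, and link it to objective 3. Do not require significance on both references, and do not dichotomise at 0.80; step 5 of the working shows the loss of power from dichotomising.
3. In the Protocol Summary, call SPECT a comparator. Where a 6-month SPECT is done, report whether the baseline defect persisted. Objective 5 keeps SPECT as its reference.

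The cost is wording and an additional analysis of data already collected, with no extra procedure. There are two downsides. The 6-month data cover only about 58–80 patients who were not revascularised, selected partly by the tests under study, and this must be reported as a limitation. The IMR claim also becomes harder to support.

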If TAVI/SAVR results in a significant improvement in LV remodelling and microvascular function, it should be expected that the current invasive gold-standard for measuring microvascular resistance (IMR; index of microcirculatory resistance) would improve several months after the valve intervention. If this is the case then the FFR measurement should be more accurate (as it is in patients without aortic stenosis). The question is whether a pre-TAVI/SAVR index (based on a combination of FFR and IMR) could be used in the future for assessing intermediate lesions in these patients. Developing a “corrected” FFR measurement of intermediate coronary artery lesions based on the presence or absence of microvascular dysfunction would be very useful in the pre-operative work-up of patients with aortic stenosis and would have important prognostic implications. This will be accomplished by first determining the FFR 6 months after intervention (TAVI or SAVR), when it is anticipated that the microvascular function would have returned to normal, and comparing this with the FFR prior to the intervention to determine if there is a significant change in the FFR after intervention. At the same time microvascular function will be assessed in order to develop a “corrected” FFR, which can be used in the future to determine whether or not coronary lesions need to be revascularized in patients with aortic stenosis.

The theoretical model of a serial stenosis by the AS and the coronary narrowing in our study is explained in the figure 1 in the publication of Zelis et al. It is expected that the FFR will indeed decrease after TAVI and that there will be an acute (change of intercept) and chronic (change of slope) effect of the procedure on the coronary resistance. To separate these two issues we will try to measure the FFR immediately after TAVI and 6 months after TAVI. In addition the left ventricular filling pressure/ end-diastolic pressure (LVEDP) will be measured during the TAVI procedure immediately before and after valve implantation. The measurement (the delta LVEDP) will be an important marker of the “intercept” that changes acutely. To make sure the measurements of IMR, FFR and RFR are correct these will be performed twice and an average value will be used. This will also allow us to test the reproducibility.

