## 1. STUDY OBJECTIVES

### Primary outcome

1. Null hypothesis: TAVI/SAVR does not result in a significant change in FFR/RFR 6 months after intervention (Figure 1).
  - a. If the null hypothesis is upheld, this suggests that FFR/RFR measurements in patients with AS is valid even in the presence of severe AS.
  - b. If there is a significant decrease in FFR/RFR 6 months after aortic valve treatment, this suggests that the use of FFR/RFR to evaluate intermediate lesions in patients with severe AS is not valid and requires further investigation.

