## 9. STATISTICS AND ANALYSIS

### 9.1 Sample Size

The sample size for the ***primary objective*** (change in FFR after aortic valve intervention) is based on previous measurements of FFR in patients with aortic stenosis, where a standard deviation of the data was reported. An expected mean FFR of 0.82 with a standard deviation of 0.08 was used in the calculation. Fifty eight (58) patients with pre- and post-interventions catheterizations will be sufficient to detect a reduction in the FFR from 0.82 to 0.79 with an alpha level of 0.05 and power of 0.80. A total sample of 100 patients with baseline measurements of which 80 patients will undergo (T)AVR without revascularisation (20% will undergo revascularisation) and in this way are eligible for pre-and post-intervention catheterization will allow for a 25 % drop-out during the follow-up phase of the study. Missing values will predominantly be at random. Therefore, the primary endpoint will be assessed using complete case analysis. To account for missing values, the number of patients will be increased from 58 to 80 (since missing data will be excluded from analysis).

For the ***secondary objective*** (comparison of FFR versus RFR): approximately 10-20% will have left main CAD, triple vessel disease, prior myocardial infarction or tandem lesions and will not be eligible for SPECT. One Hundred patients with baseline measurements will allow a 20% drop-out to end up with 80 patients with both baseline SPECT and invasive measurements. Yamanaka *et al.* found that a sample of 80 patients was necessary to determine the optimal cutoff value of iFR for indicating myocardial ischemia. Since RFR and iFR have an extremely high correlation (0.99), the same number of patients (80) is expected to achieve an area under the ROC curve of 0.70 with 0.90% power at a significance level of 0.05 in a 2-sided test.

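### The 6-month FFR/RFR change is measured only in unrevascularised lesions, selected partly on baseline FFR, so the validity and corrected-FFR conclusions reach too far and selection alone can produce a fall

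*Combined protocol and SAP*

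**What the plan says.** Section 9.1 defines who is measured twice: "80 patients will undergo (T)AVR without revascularisation (20% will undergo revascularisation) and in this way are eligible for pre-and post-intervention catheterization". Section 3.8 (Methodology) agrees: residual coronary disease is reassessed in patients who were not revascularised immediately. The same section says that the Heart Team decides on revascularisation using the intracoronary measurements and SPECT.

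The conclusions carry no matching limit. Under Study Objectives (Primary outcome), if the null is upheld, "this suggests that FFR/RFR measurements in patients with AS is valid even in the presence of severe AS"; Expected outcomes repeats this. For the corrected FFR, the Background states the intended use as one "which can be used in the future to determine whether or not coronary lesions need to be revascularized in patients with aortic stenosis". A similar statement about it stands in the Protocol Summary, which adds that "Fewer of these patients will unnecessarily undergo coronary artery bypass grafting or stenting when the CAD does not need to be treated".

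Section 9.2 plans paired tests of FFR, RFR and IMR before and 6 months after valve treatment. It does not say how the corrected FFR is derived, over what baseline range it applies, or how revascularised patients enter any analysis of change. Section 9.1 specifies a complete-case primary analysis.

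**The concern.** Over-calling concerns lesions that the index called positive. Those that were treated have no 6-month value, so any estimate of over-calling from the paired data comes from the positive lesions that the Heart Team chose to leave. A correction fitted to 6-month FFR has no follow-up data for the treated lesions, yet its stated use is to decide which lesions to treat.

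The primary test is affected too. If low baseline values are preferentially removed, the remaining baseline mean is raised partly by chance, and the 6-month mean tends to drop back even when nothing has changed. That drop is in the direction the plan expects, and the plan would read it as evidence that FFR is not valid in severe AS.

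**Working it through.** **Inputs from section 9.1.** "An expected mean FFR of 0.82 with a standard deviation of 0.08 was used in the calculation"; the aim is to "detect a reduction in the FFR from 0.82 to 0.79 with an alpha level of 0.05 and power of 0.80"; "Fifty eight (58) patients with pre- and post-interventions catheterizations will be sufficient". The plan expects 20% to be revascularised and 25% to drop out. The conventional FFR cut-off of 0.80 or below is in the Background.

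**Assumptions added here.** FFR is bivariate normal with the same mean and SD at both visits. There is one lesion per patient. The between-visit correlation r lies between 0.5 and 0.9.

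**1. The plan's own figure.** A paired t-test, two-sided 0.05, difference 0.03 and SD of the change 0.08, has power 0.802 at n = 58 and 0.795 at n = 57, so 58 reproduces. Dropout: 58/0.75 = 77.3, so 78, consistent with 80 (80 × 0.75 = 60). The plan does not say whether 0.08 is the SD of single values or of the change. SD of change = SD × √(2(1 − r)), so the two coincide at r = 0.5.

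**2. How many positive lesions remain.** P(FFR ≤ 0.80) = Φ((0.80 − 0.82)/0.08) = Φ(−0.25) = 0.401, about 40 of 100. If all 20 revascularised patients come from these, 40 − 20 = 20 of 80 deferred patients are positive (25%), or about 15 of 60 pairs. If 0.82 (SD 0.08) already describes the paired cohort, the figure is 0.401 × 60, about 24.

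**3. Baseline shift if the lowest 20% on FFR are removed.** The cut is 0.82 − 0.842 × 0.08 = 0.753. The remaining mean is 0.82 + 0.08 × 0.280/0.80 = 0.848, a shift of 0.028.

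**4. Spurious fall with no true change.** Expected fall = 0.028 × (1 − r). Simulated values, with the rejection rate of a nominal 5% test at n = 58:

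| r | Mean change | SD of change | Rejection rate |
|---|---|---|---|
| 0.5 | −0.014 | 0.076 | 28% |
| 0.7 | −0.008 | 0.060 | 18% |
| 0.8 | −0.006 | 0.050 | 14% |
| 0.9 | −0.003 | 0.035 | 9% |

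For a fixed 20% removed, taking the lowest values gives the largest baseline shift. If the decision were unrelated to baseline FFR, the spurious fall would be zero.

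**5. Why a split at 0.80 is not a remedy.** With no true change and no removal, the group at or below 0.80 has mean 0.82 − 0.08 × 0.387/0.401 = 0.743, so it rises by 0.077 × (1 − r), or 0.008 to 0.039. The group above 0.80 falls by 0.005 to 0.026. A stratified table would show apparent over-calling and apparent missed disease from regression to the mean alone. With 15 pairs and SD 0.08, the 95% half-width is 2.145 × 0.08/√15 = 0.044, wider than the 0.03 effect.

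The plan gives no mean or SD for RFR, so the same calculation cannot be done for it.

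**The case against.** A reader might infer that the trial cannot show over-calling at all. The documents do not support that, for three reasons.

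- On the plan's own figures about 15 of 60 pairs (24 on the other reading of 0.82) are FFR-positive at baseline and are re-measured, so a rise above 0.80 can be seen, though in a small and selected group.
- The planned baseline comparison of FFR and RFR with SPECT needs no 6-month value. Section 9.1 attributes its losses to SPECT ineligibility, not to revascularisation, so it can show index-positive, SPECT-negative lesions in patients who are treated later.
- The Background's reported ischaemia cut-offs in AS suggest over-calling for a resting index (iFR 0.82 against 0.89) but under-calling for FFR (0.83 against 0.80).

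A reader might also assume that every lesion at or below 0.80 is treated, leaving no positive pairs. That needs about 40 revascularisations per 100 patients, against the stated 20%.

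It is also fair to say that the 6-month part is aimed mainly at missed disease: FFR is expected to fall, and IMR is meant to correct values that read too high. Deferred lesions are the relevant group for that question. The Protocol Summary sentence goes on to cover patients who do need treatment, it describes future benefit and is not an endpoint, and the objectives say only that the result suggests validity. A treated lesion cannot be re-measured untreated, and the restriction is disclosed.

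These points remove any charge that the design is wrong. They do not supply the missing limit on the conclusions, and they do not address selection in the primary test. An expected fall in FFR argues for calling more lesions significant, so it cannot by itself support fewer procedures. The SPECT route is partial: left main, triple-vessel and tandem disease are excluded, and it gives no data for a correction towards 6-month FFR.

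**Conclusion.** The concern holds as a limit on inference. The 6-month comparison covers lesions left unrevascularised after a decision that used baseline FFR, RFR and SPECT. It cannot estimate over-calling without bias, gives no 6-month support for a corrected FFR in revascularised lesions, and may show a fall that selection produced.

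The size is about 0.003 to 0.014 against a planned 0.03, with a false-positive rate of 9% to 28% in place of 5%. This rests on normality, one lesion per patient, an assumed correlation of 0.9 to 0.5, 0.82 (SD 0.08) applying to all 100 patients, and selection of the lowest 20% on FFR alone. The last is a limiting case: the Heart Team also uses SPECT, which would be expected to weaken the link with FFR. Averaging duplicate readings reduces only same-session noise and does not remove the effect. Figure 1 was not available and may add detail on patient flow, but the text of sections 3.8 and 9.1 is explicit.

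**What to change.** 1. Limit the conclusions under Primary outcome and Expected outcomes, and the corrected-FFR statements in the Protocol Summary and Background, to unrevascularised lesions within the baseline FFR/RFR range observed in the paired cohort.
2. Drop the Protocol Summary statement on unnecessary procedures, or base it only on the planned baseline FFR/RFR versus SPECT comparison in all SPECT patients, including those later revascularised.
3. Tabulate baseline FFR, RFR and SPECT for revascularised beside deferred patients.
4. Add to section 9.2 a sensitivity analysis of the primary change that accounts for selection on baseline. One option is a likelihood-based repeated-measures model using all baseline values, with SPECT included. State that it assumes the missing 6-month values depend only on the recorded baseline data, and that it extrapolates below the observed baseline range.
5. If change is shown by baseline FFR above and below 0.80, do not interpret it without allowing for regression to the mean.

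None of this alters procedures, sample size or clinical decisions. The cost is a narrower claim, one table and a little more analysis.
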